Standard At-Home Conservative Therapy: Mometasone nasal rinse, mouth taping, nasal strip, lateral positional therapy. Risk of *Mometasone* include systemic absorption of the topical glucocorticoid rinse and risk of aggravating cataract and glaucoma. Risk of the *mouth taping* and *nasal strip* include skin irritation from the adhesive. Risk of *lateral positional therapy* include shoulder and hip pain during the day after sleeping.

Benefits of both treatment interventions include a reduction or cessation of snoring, leading to an improvement of quality of life for both the participant and their sleeping partner.

The consent process informs a volunteer about the study, indicates that participation is voluntary, and that he/she has the right to stop at any time. Risks are listed in the informed consent form and described orally during the consent process.

2.g Early Withdrawal of Participants

Participants may withdraw at any point in the study. The Principal Investigator can also withdraw a participant at his discretion if he determines the participant is not using the intervention correctly, for failure to adhere to the intervention, or for undermining integrity of the study.

If a participant decides to withdraw from all components of the research study, the investigator will discontinue all the current and scheduled research activities in the study.

2.h When and How to Withdraw Participants

A participant can withdraw consent for the study at any time. Participants will be allowed to end participation in the study at any point should they desire. All participants will have an exit interview to ascertain any adverse effects and discuss the reason for ending participation. The study team will follow them for safety reasons up to 30 days after stopping use of the study intervention.

2.i Data Collection and Follow-up for Withdrawn Participants

If a participant has ended participation, the only data that will be collected are the data from the exit interview and the data collected prior to withdrawal. There will not be any other follow-up or data collected from these subjects.

Data collected up to this point will not be used in the analysis, and further data will not be collected from these participants.

D3 Study Intervention

3.a Description

3a.1 Interventional Arm

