There will be check-ins with the study participants every two weeks conducted through the participant's preferred communication method (i.e., phone call or video call) to answer questions and ensure participants are adhering to protocol requirements. Participants will be asked to keep a paper calendar for daily notes of side/adverse effects and study barriers. The paper calendar will be mailed back to the RA after study completion, or a photo of the paper calendar will be sent attached to an email to the RA. Treatment compliance data and rates of side effects will be collected in the two groups. Collection of compliance will occur through a nightly log of compliance, which the participants will receive via REDCap from the research team and fill out throughout the study.

3.f Prior and Concomitant Therapy

Participants will not qualify for the study if they are on any concomitant therapy for snoring not assigned by the study team. Participants who have tried prior therapy for the treatment of snoring will be eligible for the study. Information will be gathered on their use of prior or current therapies when determining study eligibility.

3.g Packaging

All packing of material will consist of the consumer packaging for all interventions except for the Mometasone. AdvancedRx will ship the participants the Mometasone via UPS or FedEx delivery directly to the participant's home.

3.h Blinding of Intervention

The Principal Investigator will conduct a pre-randomization visit with all participants in which he will explain both interventions to the participants and conduct a physical

exam. The physical exam will ensure the participants are in adequate physical health to tolerate both interventions and lack nasal polyps, temporomandibular joint disorder, and structural abnormalities. After this, the Principal Investigator will leave the visit and the other members of the study team will randomize the participants. This blinds the Principal Investigator to the intervention.

Before data analysis begins, [name] will download the data and anonymize the data into “A” and “B” groups. Only [name] will know which group belongs to which. The research team will then proceed with data analysis.

3.i Receiving, Storage, Dispensing and Return

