- Events that result in such a condition where the participants may require immediate hospitalization or increase the duration of hospitalization.
- Any events that lead to a permanent or temporary physical disability in the body of the participants. Any sort of incapacity is also regarded as SAE.
- Any events that lead to any type of congenital abnormalities. It also includes any cases of birth defects resulting from the clinical trials.
- Any events where an investigator or team of investigators finds feel that it can lead to significant hazards.

7.c Classification of Events

7c.1 Relationship

An AE or SAE may or may not be causally related to the study intervention. A causal relationship means that the intervention caused (or is reasonably likely to have caused) the AE. This usually implies a relationship in time between the intervention and the AE (e.g., the AE occurred shortly after the participant received the intervention). For all AEs, it is the responsibility of the Principal Investigator who examines and evaluates the participant to determine the relatedness of the event to the study intervention.

7c.2 Severity

Severity refers to the intensity of a specific event and is a matter of individual clinical judgment.

- Grade 1: Asymptomatic or mild symptoms; clinical or diagnostic observations only; no intervention indicated
- Grade 2: Moderate; minimal, local, or noninvasive intervention indicated; limiting age-appropriate instrumental activities of daily living (ADL)
- Grade 3: Severe; or medically significant but not immediately life-threatening; hospitalization or prolongation of hospitalization indicated; disabling; limiting self-care ADL
- Grade 4: Life-threatening; urgent intervention indicated.
- Grade 5: Death related to an AE

7c.3 Expectedness

An adverse event or suspected adverse reaction is considered "unexpected" if it is not consistent with the risk information described in this protocol or on the informed consent or is not listed at the specificity or severity that has been observed; or, if an investigator

brochure is not required or available, is not consistent with the risk information described in the general investigational plan or elsewhere in the current application, as amended.

7.d Data Collection Procedures for Adverse Events

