To date, there is no study reporting the rate of response in participants using MAD. Due to lack of preliminary data and effect size, estimates of the sample size for this study will be determined based on feasibility. We propose a pilot study with a total sample size of 60 subjects (snorers only). The sample size of 60 subjects is feasible, given the incidence of primary snoring prevalence in America, which is estimated at 40-50%¹⁵. Using a 33% drop out rate, we estimate that the sample size of 60 subjects randomized in a balanced way between the two treatment groups will provide us with 40 evaluable cases. We hypothesize that the rate of the responders in the MAD group will be 20% higher than the rate of responders in the active control group. If the rate of response in the control group is 30%, the sample size of 20 subjects per group will allow us to estimate a 95% confidence interval around the rate difference between groups with a margin of error of 30%.

F2 Interim Monitoring and Early Stopping

Due to the size of the study and the nature of a pilot study, we will not be participating in early stopping or interim monitoring of the participants.

F3 Analysis Plan

A Per Protocol analysis will be used for the primary analysis of the data. Descriptive statistics will be used to describe the characteristics of participants in the 2 study groups. Responder rate difference will be calculated as shown below:

Responder Rate:

$$\text{Responder}_{\text{Conservative}} / \text{Total Participants}_{\text{Conservative}}$$
$$\text{Responder}_{\text{MAD}} / \text{Total Participants}_{\text{MAD}}$$

Responder Rate Difference:

$$\Delta_{\text{Responder Rate}} = \text{Responder}_{\text{Conservative}} - \text{Responder}_{\text{MAD}}$$

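### The primary analysis uses an undefined per-protocol set, withdrawn participants give no end-of-study outcome, and no planned analysis shows how far the result depends on the third of pairs expected to be lost

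*Combined protocol and SAP*

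**What the plan says.** F3 (Analysis Plan) states: "A Per Protocol analysis will be used for the primary analysis of the data". No section says what adherence or completion puts a pair in that set, although 3.e collects a nightly compliance log. F3 names no other analysis population. Its responder-rate denominators are labelled only as total participants in each arm. That could be read as all randomised, but the per-protocol sentence, section 2.i and F1's 40 evaluable cases point to completers.

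Withdrawal is covered in 2.g to 2.i and 7.a:
- 2.g: "The Principal Investigator can also withdraw a participant at his discretion if he determines the participant is not using the intervention correctly", and likewise for non-adherence. It also provides for stopping all research activities: "If a participant decides to withdraw from all components of the research study".
- 2.h: "All participants will have an exit interview to ascertain any adverse effects and discuss the reason for ending participation". Safety contact continues for up to 30 days.
- 2.i: after participation ends, "the only data that will be collected are the data from the exit interview and the data collected prior to withdrawal". It then adds: "Data collected up to this point will not be used in the analysis, and further data will not be collected from these participants".
- 7.a: participants with serious adverse effects are removed from the study.

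F1 assumes 33% drop-out, so 60 pairs yield 40 evaluable, 20 per group. F4 assumes missingness at random and rules out computational adjustment, giving the small pilot size as the reason. The logistic regression or GLM in F3 explores confounders and does not bring excluded pairs back.

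**The concern.** Randomisation makes the two groups of 30 comparable. It does not do so for the 20 per arm who finish and are judged to have followed the protocol, because finishing and adhering happen after allocation and may be linked to whether the treatment works. A pair that sees no benefit has a reason to stop, and the burdens differ between arms: E4 adds maxillofacial visits for MAD, and 3a.2 requires four therapies together for conservative care. If leaving is related to response, the responder-rate difference can be too large or too small.

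The plan cannot check this. Exit interviews give reasons for leaving, but no reporting of those reasons by arm is stated, and the partner's CGI-I at the end of the study is not sought from pairs who withdraw. With no set definition, who counts as per protocol can also be settled after the data are seen.

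The stakes are those of a comparative result, even in a pilot. A2 hypothesises a statistically significant difference, F3 tests it, and A3 says the findings should help guide practice.

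**Working it through.** Differences below are MAD minus conservative; F3 writes the reverse.

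**Inputs.** 30 pairs per arm (2.d); 33% loss and 20 evaluable per group (F1); 30% response in controls and 20 points more with MAD, so 50% (F1, absolute reading).

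**The plan's own figures.** 60 × (1 - 0.33) = 40.2, so 40 evaluable. Margin of error: 1.96 × √(0.5×0.5/20 + 0.3×0.7/20) = 0.297, matching F1's 30%. F1's arithmetic is sound, but the margin covers sampling error only.

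**Dependence on the lost pairs, 10/10 loss.** Observed: 10/20 - 6/20 = +20 points. Let the lost pairs respond at rates qM and qC. The difference among all randomised is

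(10 + 10qM)/30 - (6 + 10qC)/30 = 4/30 + (qM - qC)/3.

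- qM = qC, whatever the value: 4/30 = +13.3 points.
- qM - qC = 0.20 (lost pairs differ as completers do): 0.133 + 0.067 = +20 points.
- qM = 0, qC = 1: 10/30 - 16/30 = -20 points.
- qM = 1, qC = 0: 20/30 - 6/30 = +46.7 points.
- The sign reverses only if qM - qC is below -0.40, since 0.133 - 0.40/3 = 0.

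The width of the bounds is (10 + 10)/30 = 67 points. If half the missing partners replied (an assumption), it would be 10/30 = 33 points.

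**Null rejection rate.** F3 allows chi-square or Fisher's exact test, so both are given (uncorrected chi-square, two-sided 5%, exact enumeration with fixed numbers lost). Both arms have the same true rate p. If a share f of drop-outs are non-responders and the rest respond like completers of their arm, the completer rate is p/(1 - f×d), where d is the arm's loss fraction. For example, with p = 0.25 and f = 1: 10/10 loss gives 0.375 in both arms; 13/7 gives 0.25×30/17 = 0.441 against 0.25×30/23 = 0.326; 15/5 gives 0.50 against 0.30.

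| Loss, first arm / second arm | Drop-outs that are non-responders | True rate | Chi-square | Fisher |
|---|---|---|---|---|
| 10/10 (planned) | all | 25% | about 5% | about 2.5% |
| 13/7 (assumed) | all | 15 / 25 / 30% | 9.7 / 13.1 / 15.1% | 4.6 / 7.1 / 8.2% |
| 15/5 (assumed) | all | 15 / 25 / 30% | 17.2 / 25.8 / 33.0% | 9.9 / 19.6 / 24.9% |
| 13/7 (assumed) | half | 25% | about 7% | about 3% |
| 15/5 (assumed) | half | 25% | about 8% | about 5% |

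Where there is inflation, the false difference favours the arm that loses more pairs. If drop-out is unrelated to outcome, chi-square stays close to 5% at every split. The unequal splits, the values of f and the true rates of 15% and 25% are assumptions; none is in the documents.

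**The case against.** The strongest reply is that this is a feasibility-sized pilot, that F4 says openly why nothing is adjusted, and that bounds of -20 to +47 are mechanical: any trial losing a third has bounds 67 points wide, and the ends need every lost pair to respond in one arm and none in the other. That is fair. The bounds and the 13-point figure show sensitivity, not demonstrated bias. Pilot size does not, however, explain leaving the set undefined or omitting analyses that need no extra participants.

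A second reply is that C3 measures outcomes after four weeks of the intervention and the CGI-I asks about response to treatment, so pairs who never start may have nothing to rate. This stands, and the fix allows for it. The all-randomised estimate will still be a complete-case one for whatever CGI-I is missing, and if no lost partner replies and every completer adheres, the headline number does not change.

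Some stronger readings are not supported:
- A reader might infer that the plan inflates the false-positive rate. At the planned equal split it does not, and nothing in the documents predicts which arm would lose more or by how much.
- A reader might infer that 2.i discards the partner's own daily CGI-S texts. Partners are counted as participants in their own right (2.d), and 2.i does not say whether their data go when the snorer withdraws. Nor does it say whether removals under 2.g and 7.a are covered.
- A reader might infer that investigator withdrawals could be chosen by arm. Section 3.h says of the pre-randomisation arrangement: "This blinds the Principal Investigator to the intervention". How that fits with the investigator's duties elsewhere is a separate question.
- Nor is nothing learned from people who leave: the exit interview records adverse effects and reasons.

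**Conclusion.** The concern holds as a gap in the analysis set, in outcome collection and in sensitivity analysis, and should be fixed. At F1's own rates and balanced loss, an observed +20 points is +13 among all randomised if lost pairs respond alike in both arms, and between -20 and +47 at the extremes. It stays at +20 only if the lost pairs differ between arms by the same 20 points, which is in effect what an unadjusted completer analysis assumes. No planned analysis would show which case applies.

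The effect on the test is conditional. It needs drop-out that is both unequal and outcome-related; its size then depends on the test chosen, and with Fisher's test and only half the drop-outs non-responders (25% true rate) the rate does not exceed 5%. The 10-per-arm loss is F1's overall 33% taken as balanced; actual losses may differ.

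**What to change.** 1. **F3.** Make the primary analysis all randomised pairs in the arm assigned, using every partner CGI-I obtained whatever the treatment use. Keep per protocol as secondary, with its set defined in advance from the nightly compliance log.
2. **2.g to 2.i and 7.a.** Separate stopping the intervention from withdrawing consent for data. Delete the sentence in 2.i that excludes data collected before withdrawal, subject to the consent wording, which we have not seen. State whether the partner's own data, and removals under 2.g and 7.a, are covered. Send the existing Visit 2 survey (email or telephone, E6) to every partner who has not withdrawn consent: at the scheduled end of the intervention or, for pairs who never started, at a date fixed from randomisation (H2's eight weeks is available). Record the CGI-I as not obtained where it cannot be rated.
3. **F4.** Add missing-as-non-response and best/worst case by arm as sensitivity analyses. Note that missing-as-non-response is itself biased if drop-out is unequal and unrelated to response. Report drop-out counts and exit-interview reasons by arm.

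No treatment-stopping rule changes. The cost is protocol and SAP wording, some additional surveys, and possibly a consent edit with IRB approval. Downsides: some partners will not reply, some randomised pairs may have no CGI-I, and the headline estimate no longer describes the effect under full use, which the retained per-protocol analysis still does.

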The secondary aim is to evaluate the effectiveness of treatment of snoring on the sleeping partner's sleep quality as measured by the *CGI-I* scale, the *Epworth Sleepiness Scale (ESS)*, and a modified *Symptoms of Nocturnal Obstruction and Related Events (SNORE-25)* questionnaire.

C3 Rationale for the Selection of Outcome Measures

Primary Outcome:

Clinical Global Impression of Improvement Scale (CGI-I) - Partner: To address the primary aim, the primary outcome measurement is the CGI-I Scale in the sleeping partner. The CGI-I will pose the question “Overall, how do you rate the response to snoring treatment?”, with 7 response options including: *Very Much Improved, Much Improved, Minimally Improved, No Change, Minimally Worse, Much Worse, and Very Much Worse*. The CGI-I is adapted from a previously validated measure commonly used in psychiatric studies, and is a self-report scale²¹. Participants will be measured after completing 4 weeks of their respective intervention. As snoring primarily effects the sleeping partner, the sleeping partner's responses will be the primary outcome measurement. A sleeping partner who rates the response to treatment as either *Very Much Improved* or *Much Improved* will be graded as a responder to treatment. The percentage of responders to non-responders will be compared between the two treatment arms.

Secondary Outcomes:

1. **CGI-Improvement Scale - Participant:** The CGI-I will be administered to the participant in the same method as described above.
2. **CGI-Severity (CGI-S) Scale - Partner and Participant:** The CGI-Severity Scale poses the question “On average, how much of a problem does your [partner’s] snoring pose?” The 5 response options will include: no problem, mild problem, moderate problem, severe problem, problem as severe as it can be. It will be measured both at baseline and after treatment. In addition, the CGI-S will be measured by the sleeping partner on a daily basis both before and after treatment.

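### Does the F3 formula turn the primary effect into a difference in responder counts, taken in the wrong direction?

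*Combined protocol and SAP*

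**What the plan says.** **C3 (primary outcome).** A sleeping partner who picks either of the two best of the seven CGI-I categories "will be graded as a responder to treatment". C3 then says: "The percentage of responders to non-responders will be compared between the two treatment arms".

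**F1 (sample size).** The expectation is that "the rate of the responders in the MAD group will be 20% higher than the rate of responders in the active control group". With a 30% control rate and 20 evaluable subjects per group, F1 states a 95% confidence interval for the between-group rate difference with a 30% margin of error.

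**F3 (analysis plan).** The lead-in is "Responder rate difference will be calculated as shown below". The two rates follow, "Responder}_{\text{Conservative}} / \text{Total Participants}_{\text{Conservative" and "Responder}_{\text{MAD}} / \text{Total Participants}_{\text{MAD". Under a heading that names the responder rate difference comes the line at issue: "\Delta_{\text{Responder Rate}} = \text{Responder}_{\text{Conservative}} - \text{Responder}_{\text{MAD". F3 then calls for a 95% interval around the difference and a chi-square or Fisher's exact test that covers the difference in responder rate.

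**Sections 2.e, 3.h and F5.** Data are analysed and the manuscript drafted with the arms labelled A and B. The real names replace the placeholders after all tables and figures are made.

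**The concern.** Three features of the text invite worry.

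- **Counts or rates.** In the rate lines, the symbol for responders in an arm is the numerator. The difference line uses the same symbol with nothing beneath it, so on its face it subtracts numbers of people. A count difference means little unless both arms have the same number analysed, and F1 expects to lose a third of those randomised.
- **Direction.** F1 and C1 expect MAD to do better, but the formula takes conservative minus MAD, so the expected benefit is negative. The plan does not say which sign favours MAD, and the analysts work on masked groups.
- **A third quantity.** Taken literally, responders to non-responders is an odds, not a proportion of everyone in the arm.

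If an analyst followed these lines to the letter, the headline estimate and its interval could be on the wrong scale or reported with the wrong sign.

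**Working it through.** **Inputs.** From F1: 60 randomised, 33% drop-out, 20 evaluable per group, control rate 30%, MAD rate 20% higher. I read that as 20 percentage points, so 50%, and test the relative reading below. Allocation is 1:1 (section 3.c).

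**1. Reproduce the plan's own figure.**

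- Evaluable: 60 × (1 − 0.33) = 40.2, about 40, or 20 per arm.
- Half-width for a difference in proportions: 1.96 × √(0.30 × 0.70/20 + 0.50 × 0.50/20) = 1.96 × √(0.0105 + 0.0125) = 1.96 × 0.1517 = **0.297**, which is F1's 30%.
- Pooled variance, mean rate 0.40: 1.96 × √(2 × 0.40 × 0.60/20) = 0.304.
- Relative reading, MAD rate 0.30 × 1.2 = 0.36: 1.96 × √(0.0105 + 0.36 × 0.64/20) = 0.291.

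All three round to about 30%.

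**2. Try the other two readings against the same 30%.**

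- Counts: expected difference 0.30 × 20 − 0.50 × 20 = 6 − 10 = −4 responders; half-width 1.96 × √(20 × 0.21 + 20 × 0.25) = 1.96 × √9.2 = 5.9 responders. This is a number of people, not a percentage.
- Responders to non-responders: 0.30/0.70 = 0.43 against 0.50/0.50 = 1.00, a gap of 0.57. By the delta method the variance in each arm is p/(n(1 − p)³), giving 0.30/(20 × 0.343) = 0.0437 and 0.50/(20 × 0.125) = 0.200. The half-width is 1.96 × √0.2437 = 0.97, nowhere near 30%.

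Only the difference in proportions matches what F1 planned for.

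**3. What the literal count reading would do.** Hold the true rates at 30% and 50%, with a total of 40 evaluable:

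| Conservative / MAD evaluable | Count difference | Rate difference |
|---|---|---|
| 20 / 20 | 6.0 − 10.0 = −4.0 | −0.20 |
| 22 / 18 | 6.6 − 9.0 = −2.4 | −0.20 |
| 24 / 16 | 7.2 − 8.0 = −0.8 | −0.20 |
| 25 / 15 | 7.5 − 7.5 = 0.0 | −0.20 |
| 26 / 14 | 7.8 − 7.0 = +0.8 | −0.20 |

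The mechanism is real, but two things would have to happen together. Someone would have to report a count under the label of a rate difference, and drop-out would have to be very lopsided. From 30 per arm, 25/15 means losing 5/30 = 17% against 15/30 = 50%, and 26/14 means 4/30 = 13% against 16/30 = 53%. These splits are illustrative; the plan assumes 20 and 20.

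**4. Direction.** Take 6/20 conservative and 10/20 MAD.

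- MAD minus conservative: +0.20, interval about −0.10 to +0.50.
- Conservative minus MAD: −0.20, interval about −0.50 to +0.10.
- Two-sided p-values in either order: chi-square 0.197 (without continuity correction), Fisher 0.333.

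The two intervals are mirror images of equal width. The tests work on the 2×2 table, so the denominators enter whatever the difference line says.

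**5. Masking.** While the arms are A and B, nobody on the analysis side can apply a formula with conservative and MAD subscripts in either order, so reversing it protects no one. F3 has each arm's rate calculated, and F5 puts the true names in afterwards. Two named rates show which arm did better whatever the sign of their difference.

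**The case for a change.** The strongest case for acting is that this is the only formula given for the primary effect, it is misprinted, and correction costs a sentence or two. The slip is visible on the page, the literal result at 20/20 is −4 rather than −0.20, and even a mild 22/18 imbalance moves the count from −4.0 to −2.4 while the rate difference stays put. A stated sign convention would also lower the chance of a slip when labels are restored.

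It can be added that the denominator itself is not spelled out. Ten responders are 33% of 30 randomised but 50% of 20 evaluable.

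What stands: the difference line lacks its denominators, and C3's phrase does not match F3's rate. What does not stand is the step from there to a wrong estimand. A reader would have to ignore the lead-in, the heading, the two rates directly above and the label on the left of the equation. The sign is a labelled convention, and F1 and C1 state a hypothesis rather than an order of subtraction. C3 speaks of a percentage compared between arms in a section on choosing outcome measures, and no section plans an odds as the effect measure. Who counts in the denominator is a question about the analysis population: it turns on F3's per-protocol statement and the exclusion of withdrawn participants' data in section 2.i. Writing the difference line as one rate minus the other would not answer it.

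**Conclusion.** No change to the plan is called for. The intended measure, a difference in responder proportions, is clear from F1 and F3 together, and F1's 30% margin reproduces on that scale (0.297). The missing denominators are a slip of notation, the order of subtraction is a convention, and the C3 wording is loose prose. Tidying them at a convenient time would do no harm, but it would leave the 60 subjects, the 30% margin, the chi-square or Fisher's test and the two-sided conclusion as they are.

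This rests on two assumptions. First, that the stated 20% advantage means percentage points; the relative reading gives 0.291 and the same answer. Second, that the analyst follows F3's stated definition of a rate, which is printed immediately above the line in question.
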